In addition to the above industry-initiated studies, the Lake Washington Vascular VenaSeal™ Post-Market Evaluation (WAVES) study was a single-center multiple-investigator, single-arm prospective study investigating the use of the VenaSeal™ system in patients with symptomatic VRD. The study assessed the use of the VenaSeal™ system in GSVs (n=48), SSVs (n=8), and accessory saphenous veins (n=14).³¹ Diseased veins of up to 20 mm diameter were included. The WAVES protocol did not allow adjunctive tributary treatment at the time of the index procedure which were staged at 3 months post-index procedure.

There were 70 veins treated in 50 subjects. All primary target veins (48 GSV, 14 ASV, and 8 SSV) showed 100% closure using DUS at 7 days and 1 month. Complete closure at 3 months was achieved in 70 (99%) of the treated veins. By 3 months, the revised Venous Clinical Severity Score (rVCSS) (6.5 ± 2.4 at baseline to 1.8 ± 1.4 at 1 month and 3 month; p<0.001), Aberdeen Varicose Vein Questionnaire (AVVQ) (17.3 ± 7.9 at baseline to 8.9 ± 6.6 at 1 month and 6.5 ± 7.2 at 3 month; p<0.001), and the EQ VAS (84 ± 12 at baseline to 88.3 ± 8.7 at 1 month and 88.6 ± 10.6 at 3 month; p = 0.002) all showed statistical improvement between baseline and 1 month, and baseline and 3 month visits. The percentage of patients who required adjunctive treatments at three months was lower than had been predicted by the treating physicians (65% versus 96%, p=.0002).³² Procedural pain was mild with a Nominal Pain Rating (NPR) of 2.2 ± 1.8, and the mean time to return to work and normal activities was 0.2 ± 1.1 and 2.4 ± 4.1 days, respectively.

Phlebitis was the most common AE, occurring in the treatment area or side branches in 10 patients (20%), but resolving in all but one subject (2%) by one month. One patient developed body hives within the first week of the procedure which was resolved following antihistamine and steroid treatment, this was said to be consistent with a cyanoacrylate allergy. There were no DVTs or other SAEs. One patient had a thrombus extension at the seven-day DUS which was no longer evident at the one-month DUS. Between the 1-month and 3-month visits, there was one AE, knee bursitis in the treatment limb which was determined as unrelated to the procedure.³²

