3. Change in venous disease symptoms at 7 and 30 days, and at 6, 12, 24, 36, 48, and 60 months compared to baseline (7 and 30 days, 6 and 12 months only for VenaSeal vs. Surgical Stripping Study), as measured by the revised Venous Clinical Severity Score (rVCSS) and subject self-reporting.

Hypothesis

The following hypothesis will be tested:

$$H_0: \mu_A(t) - \mu_A(0) = \mu_C(t) - \mu_C(0)$$

$$H_a: \mu_A(t) - \mu_A(0) \neq \mu_C(t) - \mu_C(0)$$

where $\mu_A(t)$ and $\mu_C(t)$ are the mean VCSS scores at time point t in the VenaSeal™ system arm and the ETA or surgical stripping arm, respectively. Time t is any of 7 days, 30 days, 6, 12, 24, 36, 48, or 60 months.

Endpoint Definition

The VCSS is a validated 10-question venous disease severity measurement intended to evaluate the responses to changes in disease severity over time and in response to treatment. Each signs / symptom can have a grade ranging from 0 (absent) to 3 (severe). The total VCSS score is the sum of all questions. The score ranges from 0 (no venous disease) to 30 (severe venous disease).

Analysis Methods

The total VCSS value at baseline, at each visit, and change from baseline will be summarized for ITT population. The comparison will be done between the VenaSeal and control (ETA or Surgical Stripping) arms. In order to test the above stated statistical hypothesis, a Wilcoxon two-sample test with t approximation will evaluate the change in the score index from baseline to time t. The analysis will be performed using SAS code similar to:

```
proc npar1way data= vcsschg Wilcoxon plots = none;
  title "Wilcoxon test of Change in VCSS scores";
  class trtGroup;
```

```
var vcssdiff;  
where cpevent="XXX";  
run;
```

Additionally, a linear mixed effects model will be fit on VCSS scores with an interaction variable fit for time and study group. Time points include baseline and scheduled follow-up visits. The model will account for the correlation of scores within each subject. Likelihood ratio tests will be used to test for the significance of the study group effect and the time effect. Partial t-tests will be used to compare scores between study groups at specific time points.

The analysis will be performed using SAS code similar to:

```
PROC MIXED;  
  CLASS time trtGroup;  
  MODEL VCSS = time trtGroup time*trtGroup;  
  RANDOM INT / SUBJ=ptid corr=exch;  
RUN;
```

Determination of Subjects for Analysis

The analysis will consist of the ITT population.

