missing responses for a question divided into left and right legs, the entire question is set to missing. For questions divided into left and right legs, some patients suffering from varicose veins in only one leg have a tendency to miss out boxes for the unaffected leg, rather than ticking the first box implying no symptoms. As a rule, if a patient misses any of the response set for one leg and having completed question 1 has not drawn in any varicose veins on the same leg, their missing responses for that one leg should be coded as zero i.e. no symptoms. Question 4 of the AVVQ was not asked in this study and therefore is excluded from the scoring. Because this question is missing, the maximum possible score is 97.783. Calculating the modified AVVQ to account for missing questions uses the following adjustment: Score = 100 * [Patient Score] / [Max Possible Score] where Patient Score is the sum of the answered questions. The scoring instructions for the AVVQ are located in the Statistical Appendices.

Analysis Methods

The total AVVQ value at baseline, at each visit, and change from baseline will be summarized for ITT population. The comparison will be done between the VenaSeal and control (ETA or Surgical Stripping) arms. In order to test the above stated statistical hypothesis, a Wilcoxon two-sample test with t approximation will evaluate the change in the score index from baseline to time t.

Determination of Subjects for Analysis

The analysis will consist of the ITT population.

5. Change in EuroQoL Group 5-Dimension Self-Report Questionnaire (EQ-5D-5L) at 30 days, and 6, 12, 24, 36, 48 and 60 months (30 days, 6 and 12 months only for VenaSeal vs. Surgical Stripping Study) compared to baseline.

Hypothesis

The following hypothesis will be tested:

$$H_0: \mu_A(t) - \mu_A(0) = \mu_C(t) - \mu_C(0)$$

$$H_a: \mu_A(t) - \mu_A(0) \neq \mu_C(t) - \mu_C(0)$$

where $\mu_A(t)$ and $\mu_C(t)$ are the mean EQ-5D scores at time point t in the VenaSeal™ system arm and the ETA or surgical stripping arm, respectively. Time t is any of 7 days, 30 days, 6, 12, 24, 36, 48, or 60 months.

Endpoint Definition

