The EQ-5D is a two-component tool consisting of a descriptive part that evaluates five dimensions (mobility, self-care, usual activities, pain/discomfort, anxiety/depression) and the EQ-VAS, a vertical, visual analog scale, used for self-reporting on health. The EQ-5D index can be calculated based on the EQ-5D-5L crosswalk from the US TTO value set. Guidance is on the EuroQol Group website (EQ-5D- 5L Value Sets): <https://euroqol.org/wp-content/uploads/2021/01/EQ-5D-5LUserguide-08-0421.pdf>.

Analysis Methods

The EQ-5D index and visual analog scale (VAS) values at baseline, at each visit, and change from baseline will be summarized for ITT population. The comparison will be done between the VenaSeal and control

(ETA or Surgical Stripping) arms. In order to test the above stated statistical hypothesis, a Wilcoxon two-sample test with t approximation will evaluate the change in the score index from baseline to time t.

Determination of Subjects for Analysis

The analysis will consist of the ITT population.

6. Change in the 36-Item Short Form Health Survey (SF-36) reported by the patient at 30 days, and 6 and 12 months compared to baseline.

Hypothesis

The following hypothesis will be tested:

$$H_0: \mu_A(t) - \mu_A(0) = \mu_C(t) - \mu_C(0)$$

$$H_a: \mu_A(t) - \mu_A(0) \neq \mu_C(t) - \mu_C(0)$$

where $\mu_A(t)$ and $\mu_C(t)$ are the mean SF-36 physical or mental health scores at time point t in the VenaSeal™ system arm and the ETA or surgical stripping arm, respectively. Time t is any of 7 days, 30 days, 6, or 12 months.

Endpoint Definition

The SF-36 is a 36-item generic QoL tool measuring health across three dimensions and including eight separate scales: 1) Functional status (including physical functioning, social functioning, role limitations attributed to physical problems, and role limitations attributed to emotional problems), 2) wellbeing (including mental health, energy and fatigue, and pain), and 3) overall evaluation of health (including general health perception). This study will report the results of the physical functioning and mental health scales.

Analysis Methods

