The SF-36 physical functioning and mental health scales at baseline, at each visit, and change from baseline will be summarized for ITT population. The comparison will be done between the VenaSeal and control (ETA or Surgical Stripping) arms. In order to test the above stated statistical hypothesis, a Wilcoxon two-sample test with t approximation will evaluate the change in the scales from baseline to time t.

Determination of Subjects for Analysis

The analysis will consist of the ITT population.

7. Change in the Venous Dependent Quality of Life (VenousDQoL) reported by the patient at 30 days, and 6, 12, 24, 36, 48, and 60 months (30 days, 6 and 12 months only for VenaSeal vs. Surgical Stripping Study) compared to baseline.

Hypothesis

There is no hypothesis test for this endpoint.

Endpoint Definition

Subjects answer their general quality of life with potential responses on an ordinal scale as follows: excellent, very good, good, neither good nor bad, bad, very bad, or extremely bad. Subjects also answer what their quality of life would be without varicose veins with potential responses on an ordinal scale as follows: very much better, much better, a little better, the same, or worse.

Analysis Methods

For each treatment arm and time point, the count and percentage of subjects with each response will be presented.

Determination of Subjects for Analysis

The analysis will consist of the ITT population.

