The EQ-5D index and visual analog scale (VAS) values at baseline, at each visit, and change from baseline will be summarized for ITT population.

Determination of Subjects for Analysis

ITT population

7. Change in the 36-Item Short Form Health Survey (SF-36) reported by the patient at 30 days, and 6 and 12 months compared to baseline.

Endpoint Definition

The SF-36 is a 36-item generic QoL tool measuring health across three dimensions and including eight separate scales: 1) Functional status (including physical functioning, social functioning, role limitations attributed to physical problems, and role limitations attributed to emotional problems), 2) wellbeing (including mental health, energy and fatigue, and pain), and 3) overall evaluation of health (including general health perception). This study will report the results of the physical functioning and mental health scales.

Analysis Methods

The SF-36 physical functioning and mental health scales at baseline, at each visit, and change from baseline will be summarized for ITT population. The comparison will be done between the VenaSeal and control (ETA or Surgical Stripping) arms. In order to test the above stated statistical hypothesis, a Wilcoxon two-sample test with t approximation will evaluate the change in the scales from baseline to time t.

Determination of Subjects for Analysis

ITT population

8. Change in the Venous Dependent Quality of Life (VenousDQoL) reported by the patient at 30 days, and 6, 12, 24, 36, 48, and 60 months compared to baseline.

Endpoint Definition

Subjects answer their general quality of life with potential responses on an ordinal scale as follows: excellent, very good, good, neither good nor bad, bad, very bad, or extremely bad. Subjects also answer what their quality of life would be without varicose veins with potential responses on an ordinal scale as follows: very much better, much better, a little better, the same, or worse.

Analysis Methods

For each time point, the count and percentage of subjects with each response will be presented.

Determination of Subjects for Analysis

ITT population

In addition, the primary endpoints of the Randomized Studies will also be assessed for the VLU Study:

9. Peri-procedural patient satisfaction from the VenousTSQe at 30 days

Endpoint Definition

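### AVVQ, EQ-5D-5L and SF-36 are compared between arms only by a Wilcoxon test on raw change, with no baseline covariate and no pre-specified adjusted difference or confidence interval.

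*SAP*

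**What the plan says.** SAP 7.9.1.7 (Patient Experience secondary endpoints), items 4 to 6, sets for AVVQ, EQ-5D-5L and SF-36 a two-sided hypothesis that the mean change from baseline is the same in both arms at each time t. For AVVQ and for the EQ-5D index and VAS, the analysis is that "a Wilcoxon two-sample test with t approximation will evaluate the change in the score index from baseline to time t". For SF-36, "a Wilcoxon two-sample test with t approximation will evaluate the change in the scales from baseline to time t". Values and changes are also summarized by visit. No covariate, adjusted estimate or interval for the treatment difference is named.

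The same section treats rVCSS (item 3) differently. It has the Wilcoxon test on change, but "Additionally, a linear mixed effects model will be fit on VCSS scores with an interaction variable fit for time and study group", and "Time points include baseline and scheduled follow-up visits".

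Protocol 10.5 and 10.8 require all three questionnaires at baseline. Protocol 10.4 stratifies randomization by site and by CEAP 2–3 versus 4–5. SAP 7.9.1.3 says p-values for these secondary objectives are not adjusted for multiplicity.

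In the single-arm VLU study, the SF-36 item (SAP 7.9.2.6, item 7) contains this sentence: "The comparison will be done between the VenaSeal and control (ETA or Surgical Stripping) arms". A two-sample Wilcoxon test follows it.

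**The concern.** Analysing raw change fixes the coefficient on baseline at 1. If the true regression slope of follow-up on baseline is below 1, subtracting the whole baseline adds noise and over-corrects any chance imbalance between arms. A slope below 1 is likely after an effective treatment, because scores become less spread out. In WAVES, AVVQ went from "17.3 ± 7.9 at baseline to 8.9 ± 6.6 at 1 month".

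Two things are at stake. Real differences in disease-specific and generic quality of life are more likely to be missed, in a trial whose stated purpose is patient experience and clinical improvement. And a Wilcoxon p-value does not estimate the mean-change contrast that the hypothesis is about.

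**Working it through.** **Plan's own figure.** There is none to reproduce: the documents give no power, SD of change or correlation for these endpoints in this trial.

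**Inputs.** SDs are from WAVES (Protocol 4.1), a single-centre, single-arm study of 50 subjects:
- AVVQ: 7.9 at baseline, 6.6 at 1 month, 7.2 at 3 months.
- EQ VAS: 12 at baseline, 8.7 at 1 month, 10.6 at 3 months.
- SF-36 scales and EQ-5D index: none given. The equal-SD row below is a generic reference.
- Correlation r between baseline and follow-up: not given; assumed 0.3, 0.5 and 0.7.

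**Formulas.** With baseline SD s0 and follow-up SD s1:
- Var(change) = s0² + s1² − 2·r·s0·s1
- Var(ANCOVA) = s1²·(1 − r²)
- Information lost = 1 − Var(ANCOVA)/Var(change)
- Efficient slope on baseline = r·s1/s0

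**Worked case (AVVQ, 1-month SDs, r = 0.5).** Var(change) = 62.41 + 43.56 − 52.14 = 53.83. Var(ANCOVA) = 43.56 × 0.75 = 32.67. Loss = 1 − 32.67/53.83 = 39%. The efficient slope is 0.5 × 6.6/7.9 = 0.42, against the value of 1 that the change score imposes. Here Var(change) is 53.83/43.56 = 1.24 times the variance of the follow-up score alone, so subtracting baseline is worse than ignoring it. With the 3-month SDs that ratio is 57.37/51.84 = 1.11.

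**Information lost by analysing change instead of ANCOVA:**

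| SDs | r = 0.3 | r = 0.5 | r = 0.7 |
|---|---|---|---|
| AVVQ, 1 month | 46.9% | 39.3% | 32.6% |
| AVVQ, 3 months | 41.1% | 32.2% | 23.6% |
| EQ VAS, 1 month | 56.1% | 50.8% | 47.5% |
| EQ VAS, 3 months | 43.2% | 34.8% | 26.8% |
| Equal SDs | 35% | 25% | 15% |

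Under normality, the rank test costs a further factor of 3/π = 0.955, about 2 to 4 percentage points.

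**Illustrative power.** Take 119 per arm (the evaluable number for closure in the ETA study), a 2-point AVVQ difference, r = 0.5, two-sided 0.05 and a normal approximation. Power goes from 56% on change to 77% with ANCOVA using the 1-month SDs, and from 53% to 70% using the 3-month SDs. The 2-point difference is an illustration, not a figure from the plan.

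**Skewed scores.** A 3-month AVVQ of 6.5 ± 7.2 on a scale bounded at 0 is not normal. Gamma-distributed scores were therefore simulated with the WAVES means and SDs, 119 per arm and a proportional 2-point benefit (an assumption that also narrows the treated arm). Power for r = 0.3 / 0.5 / 0.7 was:
- 1-month SDs: Wilcoxon on change 41/55/73%, rank ANCOVA 70/79/90%.
- 3-month SDs: Wilcoxon on change 37/49/64%, rank ANCOVA 61/68/85%.

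Rejection under no difference was near 5% for both methods.

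**VLU passages side by side.** SAP 7.9 says no hypothesis testing will be done in the VLU study, and 7.9.2.2 says none of its secondary endpoints has a formal test. Yet 7.9.2.6 item 7 specifies a comparison with control arms and refers to a hypothesis stated above, which that section does not contain. The VLU study has no control arm.

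**The case against.** The planned test is valid under randomization, and the protocol itself defines these endpoints as change from baseline. They are unpowered secondary endpoints. SAP 7.2 provides n, mean and SD for continuous outcomes, so an unadjusted mean difference and its interval could be derived from the tables. All of this stands. It makes the matter one of efficiency and pre-specification, not validity. What remains missing is any baseline-adjusted estimate and any pre-specified interval.

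Skewness makes the normal-theory percentages approximate. It does not rescue the plan, because rank ANCOVA also gained power in the skewed simulation.

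Two stronger readings are tempting and are not supported:
- **That a third to a half of the information is lost on all three instruments.** Within the assumed correlations, that range fits only the AVVQ 1-month SDs. The 3-month SDs give less, equal SDs give 15–35%, and SF-36 and the EQ-5D index have no SDs in the documents.
- **That rVCSS suffers most, because its SD falls from 2.4 to 1.4.** Applying the change-score arithmetic there ignores the mixed model already in item 3. That model's partial t-tests compare follow-up scores between arms directly, so they do not add baseline noise. The model does lack baseline adjustment, but the change-score loss does not describe it.

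**Conclusion.** The concern holds for AVVQ, EQ-5D-5L and SF-36 as a moderate inefficiency and a missing estimate. The direction is secure: the change score has larger variance than ANCOVA unless the slope on baseline is 1, and every scenario examined shows a loss. The size is not secure. It runs from 15% to 56% across the scenarios and rests on an assumed correlation, approximate normality and SDs from one small study at 1 and 3 months, while the trial tests visits out to 60 months. No primary or key secondary conclusion is affected.

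The two-arm test in the single-arm VLU section is a separate internal contradiction that needs no assumption.

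**What to change.** - **SAP 7.9.1.7, items 4–6:** make the between-arm analysis an ANCOVA of the follow-up score on arm, baseline score and CEAP stratum (2–3 versus 4–5), with rank ANCOVA if scores are skewed. A longitudinal model with baseline as covariate is an alternative. Report the adjusted mean difference with 95% CI and keep the Wilcoxon test on change as a sensitivity analysis.
- **Item 3 (rVCSS):** add baseline adjustment to the existing mixed model, with baseline as a covariate instead of one of the outcome times.
- **SAP 7.9.2.6, item 7:** delete the two-arm comparison and Wilcoxon sentences and keep the descriptive summaries.

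The cost is SAP wording and reprogramming of four secondary endpoints. No new data are needed, because baseline scores and CEAP stratum are already collected.

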- Pain score will be collected during the index procedure and at 7 days and 30 days.
- Return to work and return to normal activities will be assessed at follow-up visits until the subject has returned to each.
- The VenousDQoL consists of two stand-alone questions at baseline, 7 and 30 days, 6, 12, 24, 36, 48 and 60 months (data will be collected through 12 months for subjects enrolled in VenaSeal vs. Surgical Stripping Study).

Questionnaire completion by delegated site personnel

The required study questionnaires such as EQ-5D-5L, VenousTSQ, patient reported symptoms, etc. should be completed in a consistent manner throughout the study. Selecting to complete the required questionnaire on behalf of the subjects should only be if the subjects require it (e.g., vision or literacy issues) and not simply by site or patient preference. The site personnel completing the questionnaire

Medtronic Business Restricted

CONFIDENTIAL

056-F275, v B Clinical Investigation Plan Template

cannot be the treating physician or the PI in order to avoid any bias. If site personnel are assigned to complete the questionnaire on behalf of the subject for one visit, then site personnel should complete for all the remaining visits. Site personnel have to read the complete questionnaire including all the response options. Ideally, the same person will complete the questionnaire with the same subject each time, if at all possible. The questionnaires completed by site personnel may differ from subject questionnaires and may require IRB/EC approval. If necessary, due to COVID-19 restrictions, these questionnaires could also be completed and signed by the subject within 24 hours prior to the follow-up visit. If captured in this manner, care must be taken to ensure the questionnaires are completed and returned to the site prior to the completion of the rest of the visit.

Healthcare Utilization

This study will collect healthcare utilization data related to subject's VRD and care related to the VenaSeal™ closure system to demonstrate total costs over the follow-up period. Specifically, this study will collect:

- Number and type of adjunctive treatments (phlebectomy and sclerotherapy) conducted through 60 months post-index procedure.

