7.9.1.3 Secondary Endpoints

Data supporting the following endpoints will be collected for both the CEAP 2-5 Randomized Studies. When appropriate, data will be evaluated for the CEAP 2-5 Randomized Studies to compare the VenaSeal™ system to surgical stripping or ETA. Data may also be pooled for all VenaSeal™ system subjects from the CEAP 2-5 randomized studies and VLU study as appropriate.

Data from VenaSeal vs. Surgical Stripping Study will be collected through the 12-month visit.

The secondary endpoints will provide additional clinical evidence related to effectiveness, safety, and patient and provider experience. The p-values from any pre-specified hypothesis tests of the remaining secondary objectives will not be adjusted for multiple comparisons. Reports or publications that contain these p-values will state that an appropriate multiple comparisons adjustment was not performed.

Descriptive statistics for the secondary endpoints will be provided. For categorical variables, the count and percentage of subjects with each outcome will be presented. For continuous variables, summary statistics (mean, standard deviation, median) will be presented. More analysis methodology details are provided below.

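### VenousDQoL is defined as change from baseline, but the SAP tabulates only the responses at each time point, so within-subject change is not estimated

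*SAP*

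**What the plan says.** SAP 7.9.1.7 item 7 names the endpoint "Change in the Venous Dependent Quality of Life (VenousDQoL) reported by the patient at 30 days, and 6, 12, 24, 36, 48, and 60" months, and the heading goes on to make baseline the reference. Protocol 5.2.3, endpoint 18, and SAP 4.2.2 say the same. The definition under item 7 lists the response options of the two ordinal questions and no change variable. On testing, the SAP says "There is no hypothesis test for this endpoint". The analysis is one sentence: "For each treatment arm and time point, the count and percentage of subjects with each response will be presented". The analysis population is ITT.

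For the VLU Study, SAP 7.9.2.6 item 8 also names change from baseline and plans: "For each time point, the count and percentage of subjects with each response will be presented".

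The general rule in SAP 7.9.1.3 adds nothing on change: "For categorical variables, the count and percentage of subjects with each outcome will be presented". SAP 7.2 and 7.9.2 are to the same effect.

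The treatment of AVVQ in the same section is different: "The total AVVQ value at baseline, at each visit, and change from baseline will be summarized for ITT population".

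Baseline data will exist. Protocol 10.5 says "The VenousDQoL consists of two stand-alone questions at baseline, 7 and 30 days, 6, 12, 24, 36, 48 and 60 months", and Protocol 10.8 lists VenousDQoL among the baseline items.

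**The concern.** The stated method does not produce the stated endpoint. Change compared to baseline is a quantity for each subject, or at least a paired summary over the same subjects. A frequency table at each visit gives only the distribution of answers at that visit. A reader who wants to know how many subjects improved after treatment, and how many got worse, cannot recover it from a series of such tables.

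There is also a possible second problem. SAP 7.4 rules out imputation for objectives other than the primary endpoints unless otherwise specified. If subjects without an answer simply drop out of the table, the baseline and later tables describe different sets of people. At stake is the interpretation of one secondary patient-experience endpoint in each of the three studies.

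**Working it through.** **Step 1: compare the five endpoints in SAP 7.9.1.7 whose names begin with change.**

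| Endpoint | Named as change from baseline | Change from baseline summarized |
|---|---|---|
| rVCSS (item 3) | yes | yes |
| AVVQ (item 4) | yes | yes |
| EQ-5D-5L (item 5) | yes | yes |
| SF-36 (item 6) | yes | yes |
| VenousDQoL (item 7) | yes | no |

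SAP 7.9.2.6 (items 4 to 8) shows the same pattern for the VLU Study. The AVVQ text also names baseline among the values to be shown. The VenousDQoL text says only time point, so even a baseline table is implied rather than promised. The documents give no sample size, power or effect figure for VenousDQoL, so there is no stated number to reproduce.

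**Step 2: do tables at each visit identify change?** Take one arm of the ETA study, 264/2 = 132 subjects, none lost, with responses grouped as favourable or unfavourable. Suppose 66 of 132 are favourable at baseline.

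- Case A: nobody changes. At 6 months 66 of 132 are favourable.
- Case B: all 66 unfavourable subjects improve and all 66 favourable subjects worsen. At 6 months 66 of 132 are favourable.

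The planned tables are identical; the shift tables are opposite. This needs no dropout.

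**Step 3: what could dropout add?** This is illustration only. Let p be the favourable share at baseline, d the share lost, and f the share of those lost who were favourable at baseline. If no subject changes, the apparent shift is (p − d·f)/(1 − d) − p. The documents give 7% attrition at 30 days for VenousTSQ (Protocol 14.1.1) and 10% at 6 months for closure (14.1.2). The values p = 0.5, f, and losses of 20% and 30% are assumptions.

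| d | f = 0.5 | f = 0.25 | f = 0 |
|---|---|---|---|
| 7% | 0 | +1.9 | +3.8 |
| 10% | 0 | +2.8 | +5.6 |
| 20% | 0 | +6.25 | +12.5 |
| 30% | 0 | +10.7 | +21.4 |

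Entries are percentage points. For d = 10% and f = 0.25: (0.5 − 0.025)/0.9 − 0.5 = 0.028.

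A second set of assumptions starts with 30% in the unfavourable categories and no true change.

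- Losing 30% of them and 15% of the others gives 0.30·0.70/(0.30·0.70 + 0.70·0.85) = 0.210/0.805 = 26.1%, an apparent fall of 3.9 points.
- Losses of 40% and 20% give 0.30·0.60/(0.30·0.60 + 0.70·0.80) = 0.180/0.740 = 24.3%, a fall of 5.7 points.

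In these examples the retained subjects also had 26.1% and 24.3% unfavourable at baseline, so a paired table would correctly show no change.

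The first column of the table is the important one: if loss is unrelated to response, the shift is zero.

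**The case against.** The strongest reply is that this is one descriptive secondary endpoint, deliberately left untested, and that counts and percentages are the SAP's standing rule for categorical outcomes. If baseline is tabulated as a time point, which the SAP neither states nor excludes, the tables show the net movement in the distribution. That much stands: what is missing is within-subject change, not all information about change.

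Three stronger readings are tempting, and the documents do not support them.

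- **A reader might infer that dropout will distort the tables.** That requires loss related to response, and nothing in the documents shows it. Protocol 6.2 says only that the 48- and 60-month visits may see more attrition, and says so to justify remote visits. Protocol 10.10 includes VenousDQoL among the assessments that can be completed remotely at those visits. The stripping study ends at 12 months, so late attrition does not arise there. SAP 7.4 requires the number analysed to be reported, so losses would be visible, though not corrected. That attenders form the denominator is itself an inference, because item 7 does not define it.
- **A reader might infer that the arms cannot be compared.** They can: the tables are by arm at each time point, and a comparison at the same visit is the randomized one. Loss common to both arms need not distort it.
- **A reader might infer that a formal between-arm model is needed.** The SAP chose no test for this endpoint. A proportional-odds model would reverse that choice, add comparisons outside multiplicity control, and may meet sparse cells on a seven-category item with 108 stripping subjects.

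A shift table is not a complete answer to missing data either. If loss depends on change after baseline, subjects with both assessments are also a selected group.

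**Conclusion.** The mismatch is real and rests on the text alone: the endpoint is change from baseline, and the planned analysis contains no measure of within-subject change in either the randomized or the VLU section. The contrast with four neighbouring endpoints suggests an omission rather than a decision. The failure to identify change holds with complete follow-up and needs no assumption.

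The dropout effect is conditional. It ranges from zero, if loss is unrelated to response, to the sizes shown above under assumed losses, and the documents do not allow a figure to be chosen.

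The consequence is small. The endpoint carries no hypothesis test, and no primary or key secondary conclusion depends on it. This is an inexpensive improvement, not a defect that threatens the trial.

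**What to change.** In SAP 7.9.1.7 item 7 and 7.9.2.6 item 8:

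1. For each of the two items and each visit named in the endpoint, add a baseline-by-visit shift table in subjects with both assessments, by arm in the randomized studies.
2. From each table give the count and percentage improved, unchanged and worsened, with descriptive 95% confidence intervals. With about 108/2 = 54 subjects per stripping arm, this three-way summary will be easier to read than the full grid for the seven-category item.
3. State the denominator, and report how many subjects lack one or both assessments.
4. State the direction of improvement. For the first item it is toward *excellent*. The second asks what quality of life would be without varicose veins, so moving from *very much better* toward *the same* means less disease impact. Say also how the option *worse* is ordered.
5. Keep the planned tables, confirm that baseline is one of the time points shown, and keep the endpoint descriptive. No proportional-odds model is needed.

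The cost is a few added tables and a short SAP edit. No new data, visits or subjects are required.
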